4.1.1.3 End of Study Visit (for Subjects *not* Continuing into the Extension Phase)

Subjects who are not continuing into the 2-year open-label Extension Phase will be followed for 30 days (± 7 days) following the last dose of study drug in the Core Phase. Once the End of Study Visit (Section 9.1.16; Table 7) has been completed, the subject may be discharged from the study.

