4.1.2 Extension Phase

Subjects who complete the 12 week Core Phase of the study, or who meet the stopping criteria as defined in Section 5.3 and are discontinued from the Core Phase, will be eligible to enter the open-label Extension Phase, if they continue to meet the inclusion criteria and do not meet any exclusion criteria for this phase of the study. Subjects and/or the subject's LAR must complete informed consent/assent in order to participate in the Extension Phase of the study.

Until the last subject completes the Core Phase and the database is locked, the Sponsor, all subjects, and all Investigators will remain blinded to treatment received in the Core Phase. Dosing of openlabel avatrombopag during the Extension Phase is described in Section 1.1.6.

Study visits will begin with Visit E-1/Month 1 which will be the same day as Visit 14 in the Core Phase. After dosing with open-label avatrombopag has been initiated during Visit E-1/Day 1, the subject should have weekly platelet counts drawn until it is determined that the subject is receiving a stable dose of avatrombopag. Otherwise, during the Extension Phase, visits will occur every 30 days for 24 months through Visit E-24/Month 24 (Figure 4).

Figure 4 AVA-PED-301: Extension Phase Study Schematic

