7.4 Drug Supplies

7.4.1 Labels and Packaging

7.4.1.1 Avatrombopag Film-Coated Oral Tablets or Matching Placebo

A sufficient supply of avatrombopag or placebo oral tablets will be provided to the clinical site. Avatrombopag will be provided as film-coated tablets, with each tablet containing avatrombopag maleate (equivalent to 20 mg of avatrombopag) and excipients. Matching placebo tablets will also be provided for the Core Phase.

During the Extension Phase, avatrombopag film-coated oral tablets will be packaged in open-label packages.

The clinical site will dispense the number of tablets required for dosing each subject for a 30 day period (e.g., a monthly supply of thirty 20 mg tablets for a 20 mg daily dose).

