9.2.3 Visit E-2 through Visit E-24

Remaining monthly visits during the Extension Phase (Visit E-2 through Visit E-24) should be conducted approximately every 30 days (±7 days).

The following assessments will be performed during each monthly visit, unless otherwise noted:

- Perform WHO Bleeding Scale Assessment (Appendix C). The Investigator should ask the subject the following question: "Have you had any bleeding or bruising since I saw you last?". This assessment should be completed prior to other visit assessments.
- Collect weight.
- Perform abbreviated PE. The abbreviated PE will consist of the following: general appearance, head, neck, eyes, ears, nose, throat, chest, lungs, heart, abdomen, extremities, joints, lymph nodes, and neurology. *The abbreviated PE should occur every 3 months while the subject is enrolled in the Extension Phase (e.g., during Visit E-4, Visit E-7, Visit E-10, Visit E-13, Visit E-16, Visit E-19, and Visit E-22).*
- Collect blood for platelet count (local laboratory) and assess need for study drug dose titration per Table 3. Note: Platelet counts are to be assessed weekly during the Extension Phase until the subject is determined to be on a stable dose of avatrombopag. Record weekly visits, dose changes, and platelet counts on the eCRF.
- Perform urine or serum pregnancy test for female subjects of childbearing potential. The pregnancy test may be performed locally and only needs to be performed every 3 months. The pregnancy test should occur only during Visit E-3, Visit E-6, Visit E-9, Visit E-12, Visit E-15, Visit E-18, Visit E-21, and Visit E-24.
- Retrieve unused study drug and record compliance in the eCRF.
- Dispense Dosing Diary for the subject to take home with instructions for completion.
- Review study drug administration with the subject and/or the subject's caregiver. Administer study drug in clinic during Visit E-6, Visit E-12, and Visit E-18 in order to confirm proper administration technique.
- Dispense 1-month supply of study drug for the subject to take at-home with instructions for administration during Visit E-2 through Visit E-24.
- Record any AEs.
- Review and record any concomitant medications, including any modifications to concomitant ITP medications.
- Discharge subject from clinic with instructions for when to return for the next clinic visit.

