9.2.4 Visit E-25/End of Study Visit – Extension Phase

The Extension Phase End of Study Visit should be performed 30 days (±7 days) after Visit E-24.

The following assessments will be performed during the Extension Phase End of Study Visit.

- Perform WHO Bleeding Scale Assessment (Appendix C). The Investigator should ask the subject the following question: "Have you had any bleeding or bruising since I saw you last?". This assessment should be completed prior to other visit assessments.
- Perform abbreviated PE. The abbreviated PE will consist of the following: general appearance, head, neck, eyes, ears, nose, throat, chest, lungs, heart, abdomen, extremities, joints, lymph nodes, and neurology.

- Collect vital signs (blood pressure, heart rate, and temperature). Vital signs should be taken after sitting for 5 minutes, whenever possible, and prior to any blood draws.
- Collect blood for platelet count (local laboratory).
- Perform urine or serum pregnancy test for female subjects of childbearing potential. The pregnancy test may be performed locally.
- Retrieve unused study drug and record compliance in the eCRF.
- Record any AEs.
- Review and record any concomitant medications, including any modifications to concomitant ITP medications.
- Discharge subject from the study.

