10.1 Adverse Events

An AE is defined as any untoward medical occurrence in a subject administered a pharmaceutical product, which does not necessarily have a causal relationship with this treatment. An AE can therefore be any unfavorable and/or unintended sign (including an abnormal laboratory finding), symptom, or disease temporally associated with the use of an investigational medicinal product, whether or not related to the investigational medicinal product. All AEs, including observed or volunteered problems, complaints, or symptoms, are to be recorded on the appropriate eCRF.

AEs, which include clinical laboratory test variables, will be monitored and documented from the time of informed consent/assent until study participation is complete. Subjects should be instructed to report any AE that they experience to the Investigator. Beginning with the informed consent/assent signature, Investigators should make an assessment for AEs at each visit and record the event on the appropriate AE eCRF. Events associated with disease progression should not be reported as AEs/SAEs. However, if in the Investigator's opinion the disease progression is manifesting in an unusual or uncharacteristic manner, the associated events should be reported as AEs/SAEs, as appropriate.

Wherever possible, a specific disease or syndrome (i.e., diagnosis) rather than individual associated signs and symptoms should be identified by the Investigator and recorded on the eCRF. However, if an observed or reported sign or symptom is not considered a component of a specific disease or syndrome by the Investigator, it should be recorded as a separate AE on the eCRF. Additionally, the condition that led to a medical or surgical procedure (e.g., surgery, endoscopy, tooth extraction, or transfusion) should be recorded as an AE, not the procedure.

Any medical condition already present at Screening should not be reported as an AE unless the medical condition or signs or symptoms present at Screening change in severity, frequency or seriousness at any time during the study. In this case, it should be reported as an AE.

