10.5 Pregnancy Reporting

If the subject becomes pregnant during the study or within 30 days of discontinuing study drug, the Investigator should report the pregnancy to the Sponsor on the Pregnancy Report Form within 24 hours of being notified.

A subject becoming pregnant while on study drug will immediately be withdrawn from the study and early termination study procedures will be performed.

The subject should be followed by the Investigator until completion of the pregnancy. If the pregnancy ends for any reason before the anticipated date, the Investigator should notify Sobi Pharmacovigilance, or its agent, by completing and forwarding the Pregnancy Report Form with the updated information within 24 hours of being notified. At the completion of the pregnancy, the Investigator will document the outcome of the pregnancy. If the outcome of the pregnancy meets the criteria for immediate classification as an SAE (i.e., postpartum complication, spontaneous abortion, stillbirth, neonatal death, or congenital anomaly), the Investigator should follow the procedures for reporting an SAE and also update the Pregnancy Report Form.

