bb For subjects who are early terminating from the study, only. Final study drug collection will occur at Visit 14 for subjects who have completed the Core Phase.

cc Adverse events (AEs) should be recorded from the time the subject/subject's legally authorized representative (LAR) signs the informed consent/assent.

Table 8 AVA-PED-301 – Extension Phase Schedule of Events

Visit	E-1 ^a	E-2	E-3	E-4	E-5	E-6	E-7 – E-24	E-25
Day	1	30 (±7 Days)	60 (±7 Days)	90 (±7 Days)	120 (±7 Days)	150 (±7 Days)	Every 30 Days (±7 Days)	720 (±7 Days)
Informed Consent/Assent ^b	X							
Inclusion/Exclusion Criteria Review	X							
WHO Bleeding Scale ^c	X	X	X	X	X	X	X	X
Vital Signs ^d	X							X
Height, Weight, BMI	X	Xe	Xe	Xe	Xe	Xe	Xe	
Abbreviated Physical Exam ^f	X			X			Xg	X
Serum Chemistry/Hematology (Central Lab)	X							
Platelet Count (Local Lab)h	X	X	X	X	X	X	X	X
Pregnancy Test ⁱ	X		X			X	X	X
Determine Appropriate Starting Dose/Assess need for Dose Titration	X	X	X	X	X	X	Х	
Administer Avatrombopag in Clinic ^j	X					X	X	
Dispense 1-month Supply of Open-label Avatrombopag	X	X	X	X	X	X	X	

BMI = Body Mass Index

^a Visit E-1 will be the first visit of the Extension Phase and the last Visit of the Core Phase (Visit 14).

^b Informed consent/assent may be performed at any time during the Core Phase for the Extension Phase.

^c WHO = World Health Organization. The following question should be asked of the subject during each visit: "Have you experienced any bruising or bleeding since I saw you last?".

^d Vital signs (blood pressure, heart rate, respiratory rate, and temperature) should be taken after sitting for 5 minutes, whenever possible. Vital signs should also be taken prior to any blood draws.

^e Weight only.

^f The abbreviated physical exam (PE) will consist of the following: general appearance, head, neck, eyes, ears, nose, throat, chest, lungs, heart, abdomen, extremities, joints, lymph nodes, and neurology.

g The abbreviated PE should be performed every 3 months while the subject is enrolled in the extension phase (e.g., Day 90, Day 180, Day 270, Day 360, Day 450, Day 540, Day 630, and Day 720).

h Platelet counts are to be assessed weekly until the subject is determined to be on a stable dose of avatrombopag. Record weekly visits, dose changes, and platelet counts on the electronic case report form (eCRF).

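### As written, a month's supply is dispensed at Visit E-24 and the child is discharged at E-25, which leaves little scheduled off-drug follow-up; the Extension passages need reconciling on the last dose

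*Protocol*

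**What the plan says.** **Extension Phase.** Section 9.2.3 instructs: "Dispense 1-month supply of study drug for the subject to take at-home with instructions for administration during Visit E-2 through Visit E-24". Table 8 marks its row "Dispense 1-month Supply of Open-label Avatrombopag" in every column up to and including E-7 to E-24, and leaves E-25 blank. On supply length, Section 7.4.1.1 states: "The clinical site will dispense the number of tablets required for dosing each subject for a 30 day period"; Section 7.4.1.2 says the same for capsules. Section 9.2.4 then states: "The Extension Phase End of Study Visit should be performed 30 days (±7 days) after Visit E-24". At that visit unused drug is retrieved, a platelet count, bleeding assessment and pregnancy test are done, adverse events are recorded and the child is discharged. No later Extension visit or contact is listed.

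**Core Phase.** Section 4.1.1.3 follows subjects who do not continue for 30 (±7) days "following the last dose of study drug in the Core Phase". Table 7 uses the same anchor, and its last column also covers early termination.

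**Reporting windows.** Contraception (8.2) runs to 30 days after the last dose. Section 10.5 requires a report "If the subject becomes pregnant during the study or within 30 days of discontinuing study drug". Adverse events (10.1) "will be monitored and documented from the time of informed consent/assent until study participation is complete". Under 10.4.1, all SAEs are reported until discharge, and after it only those the investigator considers related.

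**SAP.** Section 4.1 defines a follow-up period only for Core subjects who do not enter the Extension. The open-label period runs to early termination or end of study.

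**The concern.** Read as a site would carry them out, these instructions make E-25 an end-of-treatment visit, although it is labelled end of study. A child who stops after 12 weeks and does not continue gets about a month of scheduled off-drug observation. A child who stops after up to two years gets almost none, and no reason is given for the difference.

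At stake is safety information from the weeks after stopping. Thromboembolic and clinically significant bleeding events are the protocol's events of special interest (10.2), but they are monitored only while the child participates. A non-serious WHO Grade 2 bleed ten days after the last Extension dose would count as an event of special interest during the study, yet nothing requires it to be collected after discharge at E-25. No off-drug platelet count or bleeding assessment is scheduled, and the last pregnancy test falls on or about the last dosing day. The Extension safety tables would look complete while holding little scheduled post-treatment time for completers.

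**Working it through.** **Inputs.** Visit spacing: 30 days (4.1.2, Table 8). Last dispensing visit: E-24 (9.2.3). Supply: 30 days (7.4.1.1, 7.4.1.2). Gap from E-24 to E-25: 30 days, range 23 to 37 (9.2.4). Core follow-up: 30 (±7) days after the last dose (4.1.1.3, Table 7).

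**Step 1: reproduce the plan's calendar.** Nominal day of E-k = 30 × (k − 1) for k ≥ 2. This gives E-2 = 30, E-6 = 150, E-24 = 690 and E-25 = 720. Table 8 prints 30, 150 and 720 for E-2, E-6 and E-25, so the calendar reproduces.

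**Step 2: off-drug days at E-25 with daily dosing.** Assume the supply is taken once daily, starting on the day of E-24 (s = 0) or the day after (s = 1).

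Last dose, in days after E-24: L = min(s + 29, gap). Off-drug days = gap − L.

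| Gap to E-25 | s = 0 | s = 1 |
|---|---|---|
| 23 days | 23 − 23 = 0 | 23 − 23 = 0 |
| 30 days | 30 − 29 = 1 | 30 − 30 = 0 |
| 37 days | 37 − 29 = 8 | 37 − 30 = 7 |

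Against 30 days, the shortfall is 29 to 30 days at the nominal visit and 22 to 23 days at the late edge.

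**Step 3: less frequent regimens.** Table 4 goes down to once-weekly dosing. The last weekly dose in a 30-day period falls at most 6 days before the period ends, which adds up to 6 days: at most 6 to 7 days nominally and 13 to 14 days at the late edge. Both are below the Core minimum of 30 − 7 = 23 days.

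**Step 4: the other reading.** If the last dose were at E-24, E-25 would give 30 (23 to 37) off-drug days, as in the Core Phase. Treatment would then end at Day 690, which is 690 / 30 = 23 thirty-day months. Section 4.1.2 says "visits will occur every 30 days for 24 months through Visit E-24/Month 24", and the Extension is described as lasting two years. Dosing to Day 720 (24 × 30) fits that length better, but no legible passage states the day of the last dose.

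**Step 5: what remains reportable after discharge at E-25.**

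| Item | After discharge |
|---|---|
| SAEs judged related | Reportable (10.4.1) |
| Pregnancy within 30 days of stopping drug | Reportable, with no causality test (10.5) |
| SAEs not judged related | Not required |
| Non-serious adverse events and events of special interest | Not collected |
| Platelet count, WHO bleeding assessment | Not scheduled |

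**The case against.** The strongest objection is that the section governing this visit, 4.1.2.1, cannot be read from its start. What survives closes in the same way as the Core section 4.1.1.3, which does anchor follow-up to the last dose. A parallel sentence may stand there, and its loss from the available text is not a fault of the plan. This stands. It changes the type of problem, because such a sentence would contradict 9.2.3, 9.2.4 and Table 8 rather than leave a gap. It does not remove the need to reconcile them.

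Second, Section 9.1.16 also times Core Visit 15 from a visit (Visit 14), so the visit-based wording of 9.2.4 is not peculiar to the Extension. E-25 may be meant as the counterpart of Visit 15, with dispensing at E-24 the slip. That is possible. In the Core Phase, however, final drug collection for completers is at Visit 14, so the visit and last-dose anchors nearly coincide. They separate in the Extension only because drug is dispensed at E-24.

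Third, Table 8 is weak corroboration. Its merged E-7 to E-24 column also carries marks for procedures done only at some of those visits. This is fair, although footnotes restrict those procedures and none restricts dispensing. Section 9.2.3 names E-24 in any case.

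Fourth, a reader might infer that the Extension yields no off-drug data and that no early terminator is followed. The documents do not support that. Section 6.3.2 asks subjects who stop drug early to stay in the study for data collection, unless they withdraw consent or leave the Core Phase for lack of effect. Table 3 increases platelet monitoring while drug is stopped for a high count. The remaining gap is narrower: for those actually early terminated, Section 9.3 sets no post-dose timing and ends in discharge, and Table 8 has no early-termination column.

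**Conclusion.** The point holds as an unreconciled schedule. If the E-24 supply is taken as 9.2.3 directs, an Extension completer has 0 to 1 scheduled off-drug day at the nominal E-25 and 7 to 8 days at the late edge with daily dosing, against 23 to 37 days for Core subjects who do not continue. This assumes a full 30-day supply taken from E-24 and the Step 2 start days; once-weekly dosing lengthens the interval by up to 6 days.

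Two stronger readings should be resisted. It cannot be said that the plan omits post-dose follow-up for the Extension, because 4.1.2.1 may provide it and the last dose is not named. Nor can it be said that all post-treatment events are lost or depend on the investigator's view of causality: related SAEs are reportable after discharge, and pregnancies within 30 days are reportable whatever the cause. Adverse event and SAE collection is tied to participation and discharge; the explicit 30-day windows in 8.2 and 10.5 concern contraception and pregnancy.

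The Core efficacy analysis and the power are unaffected. This is an inexpensive improvement to safety capture and does not threaten the trial's main conclusion.

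**What to change.** Reconcile Sections 4.1.2.1, 9.2.3, 9.2.4, 9.3 and Table 8 so that they agree on when the last Extension dose occurs. Time the final Extension safety assessment relative to that dose, consistent with 4.1.1.3, 8.2 and 10.5, and state the timing for early-terminated subjects as well as completers. How long drug is dispensed stays with the sponsor.

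- If dispensing at E-24 is not intended, correct 9.2.3 and Table 8. E-25 then already serves as the follow-up and no visit is added.
- If it is intended, label E-25 as end of treatment and add a post-dose safety contact. The cost is one short contact per Extension child.

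SAP Section 4.1 needs at most a clarification that the open-label period includes this follow-up; the SAP's definition of treatment-emergent events has no end cutoff. The change is best made before children reach E-25, because off-drug observations not taken then cannot be reliably recovered.

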9.2.4 Visit E-25/End of Study Visit – Extension Phase

The Extension Phase End of Study Visit should be performed 30 days (±7 days) after Visit E-24.

The following assessments will be performed during the Extension Phase End of Study Visit.

- Perform WHO Bleeding Scale Assessment (Appendix C). The Investigator should ask the subject the following question: "Have you had any bleeding or bruising since I saw you last?". This assessment should be completed prior to other visit assessments.
- Perform abbreviated PE. The abbreviated PE will consist of the following: general appearance, head, neck, eyes, ears, nose, throat, chest, lungs, heart, abdomen, extremities, joints, lymph nodes, and neurology.

- Collect vital signs (blood pressure, heart rate, and temperature). Vital signs should be taken after sitting for 5 minutes, whenever possible, and prior to any blood draws.
- Collect blood for platelet count (local laboratory).
- Perform urine or serum pregnancy test for female subjects of childbearing potential. The pregnancy test may be performed locally.
- Retrieve unused study drug and record compliance in the eCRF.
- Record any AEs.
- Review and record any concomitant medications, including any modifications to concomitant ITP medications.
- Discharge subject from the study.

9.3 Early Termination Assessments

Should the subject early terminate from the study, the following assessments should be performed if possible.

- Perform WHO Bleeding Scale Assessment (Appendix C). The Investigator should ask the subject the following question: "Have you had any bleeding or bruising since I saw you last?".
- Perform abbreviated PE. The abbreviated PE will consist of the following: general appearance, head, neck, eyes, ears, nose, throat, chest, lungs, heart, abdomen, extremities, joints, lymph nodes, and neurology.
- Collect vital signs (blood pressure, heart rate, respiratory rate, and temperature). Vital signs should be taken after sitting for 5 minutes whenever possible and prior to any blood draw.
- Collect blood and urine for clinical laboratory tests (e.g., serum chemistry, hematology, and urine pregnancy test).
- Collect blood for platelet count (local laboratory).
- If a subject is early terminated from the study prior to the end of the PK blood draw collection in Visit 10 of the Core Phase, consideration should be given to collecting all remaining PK blood draws prior to discharging from the study.
- Record any AEs.
- Review and record any concomitant medications.
- Collect unused study drug and completed Dosing Diary.
- Discharge subject from study.

9.4 World Health Organization Bleeding Scale

Beginning with Visit 2 in the Core Phase, the Investigator should assess bleeding using the WHO Bleeding Scale (Appendix C) according to verbal responses and PE.

During Day 1/Visit 2, the following question should be asked: "Have you experienced any bruising or bleeding within the last 7 days?".

At each subsequent visit, the following question should be asked: "Have you experienced any bruising or bleeding since I saw you last?".

